#### **ADVERSE EVENTS: LIST AND REPORTING REQUIREMENTS**

Adverse event (AE) monitoring and reporting is a routine part of every clinical trial. The following list of reported and/or potential AEs (Section 7.1) and the characteristics of an observed AE (Section 7.2) will determine whether the event requires expedited reporting in addition to routine reporting.

- 7.1 **Expected Toxicities**
- 7.1.1 Adverse Events List(s)
- 7.1.1.1 Adverse Event List(s) for Mirvetuximab Soravtansine (IMGN853)

For the purposes of regulatory reporting the events listed in Table 8 are considered expected for mirvetuximab soravtansine

MedDRA SOC	SARs	Number o	f Patients Exposed N = 404	
		All SARs	Occurrence	Occurrence
			of Fatal	of Life-
			SARs	threatening
				SARs
		n (%)	n (%)	n (%)
Gastrointestinal disorders	Diarrhea $\leq$ Grade 3	137 (34)	0	0
	Nausea $\leq$ Grade 3	167 (41)	0	0
	Vomiting $\leq$ Grade 3	64 (16)	0	0
General disorders and site	Fatigue $\leq$ Grade 3	129 (32)	0	0
conditions	Asthenia $\leq$ Grade 3	45 (11)	0	0
Metabolism and nutrition	Dehydration $\leq$ Grade 3	11 (3)	0	0
disorders				
Respiratory, thoracic and	Pneumonitis $\leq$ Grade 2	34 (8)	0	0
mediastinal disorders				

#### Table 8: Mirvetuximab Soravtansine Adverse Drug Reactions (ADR)

Abbreviations: IB = Investigator Brochure; MedDRA = Medical Dictionary for Regulatory Activities; MIRV = mirvetuximab soravtansine; SAR = serious adverse reaction; SOC = system organ class.

Additional detailed information can be found in the Investigators Brochure.

#### 7.1.1.2 Adverse Event List(s) for Pembrolizumab

Detailed information on adverse events associated with pembrolizumab can be found in the Investigators Brochure.

#### 7.2 **Adverse Event Characteristics**

CTCAE term (AE description) and grade: The descriptions and grading scales found in the revised NCI Common Terminology Criteria for Adverse Events (CTCAE) version 5.0 will be utilized for AE reporting. All appropriate treatment areas should have access to a copy of the CTCAE version 5.0. A copy of the CTCAE version 5.0 can be downloaded from the CTEP web site

http://ctep.cancer.gov/protocolDevelopment/electronic applications/ctc.htm.

- For expedited reporting purposes only:
  - AEs for the agent(s) that are listed above should be reported only if the adverse event varies in nature, intensity or frequency from the expected toxicity information which is provided.
- **Attribution** of the AE:
  - Definite The AE is clearly related to the study treatment.
  - Probable The AE is likely related to the study treatment.
  - Possible The AE *may be related* to the study treatment.
  - Unlikely The AE is doubtfully related to the study treatment.
  - Unrelated The AE is clearly NOT related to the study treatment.

#### 7.3 **Serious Adverse Events**

A serious adverse event (SAE) is any AE occurring at any dose that occurs after the initial dose of study treatment, during treatment, or within 30 days of the last dose of treatment that results in any of the following outcomes:

- Death
- Is life-threatening
- Requires inpatient hospitalization  $\geq$  24 hours
- Requires prolongation of existing hospitalization •
- A persistent or significant disability or incapacity or substantial disruption of the ability to conduct normal life functions
- A congenital anomaly or birth defect

Important medical events that may not result in death, be life-threatening, or require hospitalization may be considered an SAE when, based upon appropriate medical judgment, they may jeopardize the patient and may require medical or surgical intervention to prevent one of the outcomes listed in this definition. Examples of such medical events include allergic bronchospasm requiring intensive treatment in an emergency room or at home, blood dyscrasias or convulsions that do not result in inpatient hospitalization.

Note that hospitalization is defined as admission to treat a clinical adverse event.

The following events would not be considered hospitalizations for SAE reporting purposes:

• <24-hour hold for observation, admission to a hospice facility or nursing home, respite

care, outpatient surgery, social admission (e.g., a homeless patient) or admission not associated with a precipitating clinical adverse event (e.g., elective or pre-planned surgery, or in-patient administration of subsequent chemotherapy, etc.).

Events of progression of the patient's underlying cancer as well as events clearly related to progression of the patient's cancer (signs and symptoms of progression) should not be reported as a serious adverse event unless the outcome is fatal within the safety reporting period. If the event has a fatal outcome within the safety reporting period, then the event of Progression of Disease must be recorded as an important medical event and as a SAE with CTC Grade 5 (fatal outcome) indicated.

Note: In addition to the above criteria, adverse events meeting either of the below criteria, although not serious per ICH definition, are reportable to ImmunoGen and Merck in the same timeframe as SAEs to meet certain local requirements. Therefore, these events are considered serious for collection purposes.

- Is a new cancer (that is not a condition of the study);
- Is associated with an overdose

#### 7.4 **Adverse Event Reporting to Overall PI**

- 7.4.1 In the event of an unanticipated problem or life-threatening complications treating investigators must immediately notify the Overall PI.
- 7.4.2 Investigators **must** report within 1 business day of investigator awareness to the Overall PI any serious adverse event (SAE) that occurs from the time that the subject provides informed consent, through and including the 30 calendar days after the last administration of study treatment.
- 7.4.3 Adverse Event Reporting Guidelines

All participating sites will report AEs to the Sponsor-Investigator per DF/HCC requirements, and the IRB of record for each site as applicable per IRB policies. The table below indicates which events must be reported to the Overall PI.

		DF/HCC Reportable Adverse Events(AEs)							
Attribution	Gr. 2 8 Expe	& 3 AE ected	Gr. 2 & 3 AE Unexpected	Gr. 4 AE Expected	Gr. 4 AE Unexpected	Gr. 5 AE Expected or Unexpected			
Unrelated Unlikely	Not re	quired	Not required	5 calendar days#	5 calendar days	24 hours*			
Possible Probable Definite	Not re	quired	5 calendar days	5 calendar days#	5 calendar days	24 hours*			
# If listed in prot	# If listed in protocol as expected and not requiring expedited reporting, event does not need to be reported.								

 Table 9: DF/HCC Reportable Adverse Events (AEs)

\* For participants enrolled and actively participating in the study or for AEs occurring within 30 days of the last intervention, the AE should be reported within 1 business day of learning of the event.

#### 7.5 **Reporting Period**

For the time period beginning when the consent form is signed until 30 days following cessation of treatment, any serious adverse event, or follow up to a serious adverse event, including death due to any cause whether or not related to the study products, must be reported within 24 hours to the Overall PI.

All participants with serious adverse events must be followed up for outcome.

#### 7.6 Adverse Event Reporting to ImmunoGen

The following events will be reported to ImmunoGen:

- Any serious adverse event (SAE), considered by an investigator who is a qualified physician to be related to mirvetuximab soravtansine (Section 7.6.1)
- Any new cancers or overdose of mirvetuximab soravtansine (Section 7.6.1)
- Pregnancy or Lactation (Section 7.6.2)
- Events of Special/Clinical Interest (Section 7.6.3)

#### 7.6.1 Serious Adverse Event Reporting to ImmunoGen

# For SAE reporting, including those that are expedited, the MedWatch (MW) format is preferred. A line listing is acceptable for non-expedited cases and should be sent within 2 working days to ImmunoGen using: [contact] (CC).

# IND Safety Reports (final MedWatch only) must be sent, upon submission to FDA, to: [contact]

In addition to SAE, any new cancer (that is not a condition of the study) or overdose of mirvetuximab soravtansine will be reported to ImmunoGen the same timeframe as SAEs using the procedure for SAEs.

7.6.2 Reporting a Pregnancy and Lactation to ImmunoGen

Pregnancy and lactation are exclusion criteria. The Overall PI and ImmunoGen must be immediately notified (within 24 hours) in the event of a pregnancy occurring during the course of the study and through 120 days after a patient's last dose of mirvetuximab soravtansine and through 30 days following cessation of study treatment if the subject initiates new anticancer therapy, whichever is earlier. Pregnancy is not to be reported as an AE; the pregnancy report form should be used to report a pregnancy. All reported pregnancies must be followed to the completion/termination of the pregnancy. Pregnancy outcomes of spontaneous abortion, missed abortion, benign hydatidiform mole, blighted ovum, fetal death, intrauterine death, miscarriage and stillbirth must be reported as serious events (Important Medical Events). The reporting procedures for SAE will be followed. Pregnancy outcomes listed above are also reportable to ImmunoGen in the same timeframe as SAEs. If the pregnancy continues to term, the outcome

(health of infant) must also be reported.

7.6.3 Reporting Adverse Events of Special Interest (AESI) to ImmunoGen

An adverse event of special interest (AESI) (serious or non-serious) is one of scientific and medical concern specific to the ImmunoGen product for which ongoing monitoring and rapid communication by the investigator to ImmunoGen could be appropriate. These are reportable to ImmunoGen in the same timeframe as SAEs.

#### Mirvetuximab soravtansine:

• AESI: pneumonitis.

Any symptom or sign potentially suggestive of pneumonitis should be promptly reported to ImmunoGen as for SAE, even if non-serious and/or unrelated to mirvetuximab soravtansine. If it meets requirements for expedited reporting it will be reported to the IRB and FDA per guidelines as well. These AESIs are to be reported to ImmunoGen expeditiously within 48 hours of knowledge of the event, during the study through 30 days after receiving the last dose of study treatment. It is important that the investigator provide an assessment of relationship of the SAE or AESI to study treatment at the time of the initial report. The Sponsor-Investigator's studyspecific Serious Adverse Event (SAE)/Adverse Events of Special Interest (AESI) Report Form (MW) must be used for reporting SAEs and AESIs. The contact information for reporting of SAEs and AESIs can be found on the SAE/AESI Reporting Form and Pregnancy Report Forms.

Radiologic findings suggestive of pneumonitis include new onset of any of the following:

- Pulmonary consolidation
- Pulmonary infiltrate
- Reticular infiltrate
- Nodular infiltrate
- Reticulo-nodular infiltrate
- Ground-glass pulmonary infiltrate
- Increased interstitial markings
- Interstitial infiltrate
- Honeycomb's appearance

#### 7.7 Adverse Event Reporting to Merck

The following events will be reported to Merck & Co., Inc.:

- Any serious adverse event (SAE), considered by an investigator who is a qualified physician to be related to pembrolizumab (Section 7.7.1)
- Any new cancers (Section 7.7.1) or overdose of pembrolizumab (Section 7.7.2)
- Pregnancy and Lactation (Section 7.7.3)
- Events of Special/Clinical Interest (Section 7.7.4)

7.7.1 Serious Adverse Event Reporting to Merck

Any serious adverse event, considered by an investigator who is a qualified physician to be related to Merck product that is brought to the attention of the investigator at any time following consent through the end of the specified safety follow-up period specified in the paragraph above, or at any time outside of the time period specified in the previous paragraph also must be reported immediately to Merck Global Safety.

SAE reports and any other relevant safety information are to be reported within 24 hours to the Overall PI and forwarded within 2 working days to Merck Global Safety (Attn: Worldwide Product Safety; [contact]). Following submission to Merck Global Safety, forward the SAE report and a copy of the fax confirmation to .

In addition to SAE, any new cancer (that is not a condition of the study) will be reported to Merck within the same timeframe as SAEs, using the procedure for SAEs.

#### 7.7.2 Reporting of Pembrolizumab Overdose to Merck

For purposes of this study, an overdose of pembrolizumab will be defined as any dose of 1,000 mg or greater ( $\geq$ 5 times the indicated dose). No specific information is available on the treatment of overdose of pembrolizumab. In the event of overdose, the participant should be observed closely for signs of toxicity. Appropriate supportive treatment should be provided if clinically indicated.

If an adverse event(s) is associated with ("results from") the overdose of a Merck product, the adverse event(s) is reported as a serious adverse event, even if no other seriousness criteria are met.

If a dose of Merck's product meeting the protocol definition of overdose is taken without any associated clinical symptoms or abnormal laboratory results, the overdose is reported to Merck as a non-serious Event of Clinical Interest (ECI), using the terminology "accidental or intentional overdose without adverse effect."

# All reports of overdose with and without an adverse event must be reported within 24 hours to the Overall PI and within 2 working days hours to Merck Global Safety. (Attn: Worldwide Product Safety; [contact])

7.7.3 Reporting of Pregnancy and Lactation to Merck

Although pregnancy and infant exposure during breast-feeding are not considered adverse events, it is the responsibility of investigators or their designees to report any pregnancy or lactation in a participant (spontaneously reported to them) that occurs during the study.

Pregnancies and infant exposures during breastfeeding that occur after the consent form is signed but before treatment allocation/randomization must be reported by the investigator if they cause the participant to be excluded from the trial, or are the result of a protocol-specified intervention, including but not limited to washout or discontinuation of usual therapy, diet, placebo treatment or a procedure.

Pregnancies and infant exposures during breastfeeding that occur from the time of treatment allocation/randomization through 120 days following cessation of pembrolizumab, or 30 days following cessation of treatment if the participant initiates new anticancer therapy, whichever is earlier, must be reported by the investigator. All reported pregnancies must be followed to the completion/termination of the pregnancy. Pregnancy outcomes of spontaneous abortion, missed abortion, benign hydatidiform mole, blighted ovum, fetal death, intrauterine death, miscarriage and stillbirth must be reported as serious events (Important Medical Events). If the pregnancy continues to term, the outcome (health of infant) must also be reported.

Such events must be reported within 24 hours to the Overall PI and within 2 working days to Merck Global Safety. (Attn: Worldwide Product Safety; [contact])

7.7.4 Reporting Events of Clinical Interest to Merck

#### Selected non-serious and serious adverse events are also known as Events of Clinical Interest (ECI) and must be reported within 2 working days to Merck Global Safety. (Attn: Worldwide Product Safety; [contact]).

For the time period beginning when the consent form is signed until treatment allocation/randomization, any ECI, or follow up to an ECI, that occurs to any participant must be reported within 2 working days to Merck Global Safety if it causes the participant to be excluded from the trial, or is the result of a protocol-specified intervention, including but not limited to washout or discontinuation of usual therapy, diet, placebo treatment or a procedure.

For the time period beginning at treatment allocation/randomization through 90 days following cessation of treatment, or 30 days following cessation of treatment if the participant initiates new anticancer therapy, whichever is earlier, any ECI, or follow up to an ECI, whether or not related to Merck product, must be reported within 2 working days to Merck Global Safety.

Events of clinical interest for this trial include:

- 1. an overdose of Merck product, as defined in Section 7.7.2, that is not associated with clinical symptoms or abnormal laboratory results.
- 2. an elevated AST or ALT lab value that is greater than or equal to 3X the upper limit of normal and an elevated total bilirubin lab value that is greater than or equal to 2X the upper limit of normal and, at the same time, an alkaline phosphatase lab value that is less than 2X the upper limit of normal, as determined by way of protocol-specified laboratory testing or unscheduled laboratory testing,\* whether or not related to Merck product

\*Note: These criteria are based upon available regulatory guidance documents. The purpose of the criteria is to specify a threshold of abnormal hepatic tests that may require an additional evaluation for an underlying etiology.

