## 5.7 Criteria for Taking a Participant Off Study

Patients may voluntarily withdraw from the study treatment at any time for any reason, and without prejudice to further treatment. In addition, patients may be withdrawn by the Investigator if they do not feel the patient is deriving clinical benefit or because the patient is experiencing unacceptable toxicity, patient is lost to follow up, or patient is not compliant with study procedures.

Patients who withdraw or are removed from the study treatment will have an off-treatment visit within 7 days of the decision to discontinue study treatment. The final visit will occur at the time the participant discontinues study medication. Following the Final Visit, participants will be followed for disease progression (if reason for treatment discontinuation is other than

progression) and survival, and reassessment for toxicity will be performed up to 30 days after the last treatment dose. Participants will be followed for up to 3 years by phone after removal from study or until death, whichever occurs first. Survival status should be checked every 6 months during that time

The reason for taking a participant off study, and the date the participant was removed, must be documented in the case report form (CRF). In addition, the study team will ensure Off Treatment/Off Study information is updated in OnCore in accordance with DF/HCC policy REGIST-101.

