#### 6.2 **Pembrolizumab**

AEs associated with pembrolizumab exposure, including coadministration with additional compounds, may represent an immunologic etiology. These immune-related AEs (irAEs) may occur shortly after the first dose or several months after the last dose of pembrolizumab/combination treatment and may affect more than one body system simultaneously. Therefore, early recognition and initiation of treatment is critical to reduce complications. Based on existing clinical study data, most irAEs were reversible and could be managed with interruptions of pembrolizumab/combination treatment, administration of corticosteroids and/or other supportive care. For suspected irAEs, ensure adequate evaluation to confirm etiology or exclude other causes. Additional procedures or tests such as bronchoscopy, endoscopy, skin biopsy may be included as part of the evaluation. Based on the severity of

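### Active collection of toxicity and serious adverse events ends 30 days after the last dose, although the plan expects immune-related events months later; what remains after day 30 is passive and partial

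*Combined protocol and SAP*

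**What the plan says.** **Expected timing.** Section 6.2 says that immune-related events may "occur shortly after the first dose or several months after the last dose" of pembrolizumab or the combination.

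**Active collection.** Section 5.7 says that "reassessment for toxicity will be performed up to 30 days" after the last dose, and footnote e of the Study Calendar repeats the limit. Section 7.3 puts the same limit into the SAE definition: "within 30 days of the last dose of treatment that results in any of the following outcomes". Sections 7.4.2 and 7.5 end SAE reporting to the Overall PI at 30 days. Section 7.6.3 ends reporting of pneumonitis, the adverse event of special interest, at 30 days.

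**Later follow-up.** Section 5.7 provides phone follow-up for up to 3 years with a survival check every 6 months, plus follow-up for progression in patients who stopped for another reason. It schedules no question about new adverse events.

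**Reporting beyond 30 days.**
- Section 7.7.4 makes events of clinical interest reportable to Merck over this window: "For the time period beginning at treatment allocation/randomization through 90 days following cessation of treatment", or to 30 days if the patient starts new anticancer therapy. It lists two: "an overdose of Merck product, as defined in Section 7.7.2, that is not associated with clinical symptoms or abnormal laboratory results", and "an elevated AST or ALT lab value that is greater than or equal to 3X the upper limit of normal" combined with raised bilirubin and alkaline phosphatase below twice the upper limit.
- Section 7.7.1 keeps SAEs judged related to pembrolizumab reportable outside the safety period.
- Section 7.10 requires events reported by an expedited route to be entered in the study data as well.
- Section 5.6 follows an adverse event that led to removal until it resolves or stabilises.

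**Use of the data.** Toxicity is secondary objective 2 (Section 1.3). Section 13.7.1 says when evaluability for toxicity begins but not when it ends.

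**The concern.** The plan describes a risk that extends for months and then looks for it actively for only 30 days. One drug is a checkpoint inhibitor. Section 6.1.2 says that non-infectious pneumonitis has been seen with the study drugs and can be immediately life-threatening, yet even this event has a 30-day reporting limit.

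The trial has one arm and at most 35 patients, so one or two late events would visibly change the reported toxicity profile. If they are not asked about, the profile may look more favourable than it is. With no stated end to the toxicity window, a reader of the results also could not tell which late events were sought and which were recorded only because someone happened to mention them.

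**Working it through.** The plan states no late-toxicity rate, so it has no figure to reproduce. The check sets the windows side by side and then illustrates the possible size.

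**1. Windows after the last dose or end of treatment**

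| What | Where | End | Actively sought? |
|---|---|---|---|
| Immune-related events expected | 6.2 | months | – |
| Toxicity reassessment | 5.7, Study Calendar footnote e | 30 days | yes |
| SAE definition and reporting to the Overall PI | 7.3, 7.4.2, 7.5 | 30 days | yes |
| Pneumonitis as event of special interest | 7.6.3 | 30 days | yes |
| Events of clinical interest (two types) | 7.7.4 | 90 days; 30 on new anticancer therapy | no scheduled query or test after day 30 |
| SAEs related to pembrolizumab | 7.7.1 | no end | no; depends on the investigator learning of them |
| Survival, and progression where applicable | 5.7 | up to 3 years (phone; survival every 6 months) | yes, but not for toxicity |

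**2. Length of the mismatch.** 90 − 30 = 60 days, which is 60/90 = 67% of the 7.7.4 window. Once new anticancer therapy has started, it is 30 − 30 = 0 days.

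**3. What has no scheduled collection after day 30**
- A new non-serious immune-related event that is not one of the two events of clinical interest has no scheduled route.
- A late SAE not attributed to pembrolizumab is outside 7.7.1 and past the limits in 7.3, 7.4.2 and 7.5. Section 6.2 itself says that attributing an event to one component of the combination will probably be difficult, so a route that depends on attribution is weak.
- A late SAE that is attributed to pembrolizumab has a route, but nobody is scheduled to ask about it. Section 7.7.1 also defines its safety period by pointing to a preceding paragraph in which no such period is given.
- For the hepatic event of clinical interest, the last serum chemistry on the Study Calendar is at the off-treatment visit, within 7 days of the decision to stop. After that, detection depends on unscheduled tests.

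**4. Illustration of size.** Inputs: N = 35 (Section 1.1), and p = the proportion of patients with a new immune event outside the 30-day window. The values of p are assumptions. Expected number = 35 × p. Chance of at least one = 1 − (1 − p)^35.

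| Assumed p | Expected patients of 35 | Chance of at least one |
|---|---|---|
| 1% | 0.35 | 29.7% |
| 2% | 0.7 | 50.7% |
| 5% | 1.75 | 83.4% |
| 10% | 3.5 | 97.5% |

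These are events at risk of being missed. They are not an estimate of the under-count, because some would be recorded through 7.7.1, 7.7.4 and 7.10.

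**The case against.** The strongest reply is that safety reporting does not simply end at day 30, and the documents support that reply. Section 7.7.1 keeps pembrolizumab-related SAEs reportable without an end date and also routes SAE reports to the Overall PI, and Section 7.10 brings expedited reports into the study data. Section 5.6 follows events that led to removal, Section 7.5 requires SAEs to be followed for outcome, and the Study Calendar follows ocular toxicity until it resolves. Section 13.7.1 sets no end date, so nothing excludes a late report from analysis. No decision rule uses toxicity either: Section 13.1 decides on response and progression-free survival at 6 months.

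Three stronger readings are tempting, and the documents do not support them:
- *That the 90-day duty cannot be met.* Section 7.7.4 accepts unscheduled laboratory tests. It is a duty to report what is found, not to screen. What can be said is that such events will not be found systematically.
- *That 90 days is already the plan's standard for immune toxicity.* The window covers asymptomatic overdose and one liver pattern, and it shortens on new therapy. The evidence that late immune events are expected is Section 6.2; Section 7.7.4 shows only that the windows differ.
- *That a definite number of serious events, such as 2 to 4 of 35, will be missed.* That needs an assumed rate of 5–10%, applies it to every patient regardless of new therapy, and ignores 7.7.1.

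The gap survives all of this. The later routes depend on someone volunteering the event and, for SAEs, on its attribution to pembrolizumab. Following a known event to resolution does not detect a new one.

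**Conclusion.** The point holds as a gap in active collection, not as a complete stop. After day 30, other new non-serious immune-related events and late SAEs not attributed to pembrolizumab have no scheduled collection, and those attributed to it are captured only passively. The toxicity profile may therefore under-count late immune events.

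The size cannot be derived from the documents. Under assumed rates of 1% to 10%, between 0.35 and 3.5 of 35 patients would have an event at risk of being missed. The true shortfall would be smaller to the extent that the passive routes work and that patients start new anticancer therapy early.

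The efficacy decision is unaffected. The change is worth making because it is cheap and bears directly on a stated secondary objective.

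**What to change.** 1. In Sections 5.7, 7.3, 7.4.2, 7.5 and 7.6.3 and in the Study Calendar, extend collection of SAEs and immune-related adverse events, including pneumonitis, to 90 days after the last dose, or 30 days if new anticancer therapy starts. This matches the window already in Section 7.7.4.
2. Add one phone or chart-review contact at day 90 that asks about new events and records any local liver results.
3. Correct the cross-reference in Section 7.7.1 so that the safety follow-up period is stated.
4. State the same end of the toxicity window in Section 13.7.1.

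**Cost.** One contact per patient, at most 35, with no extra clinic visit, plus amendment wording. Reported toxicity counts may rise slightly.

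**Limits.** The contact adds no laboratory test, so the hepatic pattern would still be found only where local tests were done. Ninety days is borrowed from Section 7.7.4; the documents do not show that it covers the whole period meant by "several months after the last dose of pembrolizumab/combination treatment".
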